Activated Partial Thromboplastin Time (aPTT)	$\leq 1.5 \times$ ULN unless subject is receiving anticoagulant therapy as long as PT or PTT is within therapeutic range of intended use of anticoagulants

^aCreatinine clearance should be calculated per institutional standard.

7. Female subject of childbearing potential (see appendix 14.6) should have a negative urine or serum pregnancy test within 72 hours prior to receiving the first dose of study medication. If the urine test is positive or cannot be confirmed as negative, a serum pregnancy test will be required.
8. Subjects of childbearing potential should be willing to use 2 methods of contraception for the course of the study through 120 days after the last dose of study medication (reference Section 5.5.2). Acceptable methods of birth control include: abstinence, partner with previous vasectomy, placement of an intrauterine device (IUD), condom with spermicidal foam/gel/film/cream/suppository, diaphragm or cervical vault cap, or hormonal birth control (pills or injections). NOTE: Females are considered of childbearing potential unless they are surgically sterile (they have undergone a hysterectomy, bilateral tubal ligation, or bilateral oophorectomy) or they are postmenopausal (a woman who is ≥ 45 years of age and has not had menses for greater than 1 year).
9. Male subjects without a previous vasectomy should agree to use an adequate method of contraception (i.e. abstinence, condom with spermicidal foam/gel/film/cream) starting with the first dose of study therapy through 120 days after the last dose of study therapy.
10. Subjects with urothelial carcinoma must have received a prior platinum-based regimen in the metastatic setting or have signed consent for this study within 12 months of receiving a platinum-based regimen in the perioperative setting (neoadjuvant or adjuvant).
11. Subjects with a history of diabetes mellitus must have HgbA1c level of $< 8.5\%$ upon study entry.

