9. Has active autoimmune disease that has required systemic treatment in the past 2 years (i.e. with use of disease modifying agents, corticosteroids or immunosuppressive drugs). Replacement therapy (e.g. thyroxine, insulin, or physiologic corticosteroid replacement therapy for adrenal or pituitary insufficiency, etc.) is not considered a form of systemic treatment.

10. Has known history of, or any evidence of active, non-infectious pneumonitis.
11. Has an active infection requiring systemic therapy.
12. Has a history or current evidence of any condition, therapy, or laboratory abnormality that might confound the results of the trial, interfere with the subject's participation for the full duration of the trial, or is not in the best interest of the subject to participate, in the opinion of the treating investigator.
13. Has known psychiatric or substance abuse disorders that would interfere with cooperation with the requirements of the trial.
14. Is pregnant or breastfeeding, or expecting to conceive or father children within the projected duration of the trial, starting with the pre-screening or screening visit through 120 days after the last dose of trial treatment.
15. Has received prior therapy with an anti-PD-1, anti-PD-L1, or anti-PD-L2 agent (only during Dose Expansion Phase for Cohort A).
16. Has a known history of Human Immunodeficiency Virus (HIV) (HIV 1/2 antibodies).
17. Has known active Hepatitis B (e.g. HBsAg reactive) or Hepatitis C (e.g. HCV RNA [qualitative] is detected).
18. Has received a live vaccine within 30 days of planned start of study therapy.

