5.5.2 Contraception

Pembrolizumab and vorinostat may have adverse effects on a fetus in utero. Furthermore, it is not known if pembrolizumab or vorinostat have transient adverse effects on the composition of sperm. Non-pregnant, non-breast-feeding women may be enrolled if they are willing to use 2 methods of birth control or are considered highly unlikely to conceive. Highly unlikely to conceive is defined as 1) surgically sterilized (they have undergone a hysterectomy, bilateral tubal ligation, or bilateral oophorectomy), or 2) postmenopausal (a woman who is ≥ 45 years of age and has not had menses for greater than 1 year will be considered postmenopausal), or 3) not heterosexually active for the duration of the study. Acceptable methods of birth control include: abstinence, partner with previous vasectomy, placement of an intrauterine device (IUD), condom with spermicidal foam/gel/film/cream/suppository, diaphragm or cervical vault cap, or hormonal birth control (pills or injections). Subjects should start using birth control from written informed consent throughout the study period up to 120 days after the last dose of study therapy.

Male subjects without a previous vasectomy should agree to use an adequate method of contraception (i.e. abstinence, condom with spermicidal foam/gel/film/cream) starting with the first dose of study therapy through 120 days after the last dose of study therapy.

Subjects should be informed that taking the study medication may involve unknown risks to the fetus (unborn baby) if pregnancy were to occur during the study. In order to participate in the study they must adhere to the contraception requirement (described above) for the duration of the study and during the follow-up period defined in section 7.2.3-Pregnancy and Lactation. If there is any question that a subject will not reliably comply with the requirements for contraception, that subject should not be entered into the study.

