Correlative Studies Blood Collection	x	x ⁸	x	x	x	x	x	x	x	x	x ¹⁰				

Footnotes:

¹ Procedures completed prior to consenting that are a part of a subject's standard of care may be used if they fall within the 28 day window to start treatment. Screening procedures completed 7 days of C1D1 do not need to be repeated.

² If the subject discontinues treatment due to disease progression, a phone call to the patient can serve as the Safety Follow-up Visit if the End of Treatment Visit was done. If a subject initiates a new anti-cancer therapy within 30 days after the treatment discontinuation, the 30 day Safety Follow-up Visit must occur before the first dose of the new therapy. Once new anti-cancer therapy has been initiated the subject will move into Survival Follow-up.

³ Applies to subjects who discontinue trial treatment for a reason other than disease progression. Subjects should be assessed per institutional guidelines by radiologic imaging to monitor disease status. Every effort should be made to collect information regarding disease status until the start of new anti-neoplastic therapy, disease progression, death, end of the study or if the subject begins retreatment with pembrolizumab.

⁴ Full physical exams may also be done by the investigator or qualified designee throughout participation in the trial as clinically indicated.

⁵ Only if clinically indicated and must be completed \leq 7 days prior to the first dose of study medication

⁶ It is recommended that after 1 year, imaging should be done every 6 months \pm 2 weeks; however, institutional guidelines and investigator discretion may vary.

⁷ Whenever possible, archival tissue from a tumor lesion will be obtained at screening. However, patients will be given the option to consent to a biopsy during the screening phase in case archival tissue cannot be retrieved and a second biopsy on Cycle 1 Day 14 (- 3 days). Missed tissue collection will not be considered a protocol deviation for the purposes of this study, as tissue collection is an exploratory objective for this study.

⁸ Run-in Phase, Cycle -2 Days 1 and 14

⁹ Laboratory tests for screening or entry into the Retreatment Phase should be performed within 10 days prior to the first dose of treatment. After Cycle 1, pre-dose laboratory procedures can be conducted up to 72 hours prior to dosing. Results must be reviewed by the investigator or qualified designee and found to be acceptable prior to each dose of trial treatment.

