7.1.3 Laboratory Procedures/Assessments

Details regarding specific laboratory procedures/assessments for hematology, chemistry, urinalysis, and others are specified in Table 5. The Schedule of Assessments - Section 6.0 summarizes the laboratory procedures to be performed at each visit.

Laboratory tests for screening or entry into the Retreatment Phase should be performed within 10 days prior to the first dose of treatment. After Cycle -2, pre-dose laboratory procedures can be conducted up to 72 hours prior to dosing. Results must be reviewed by the investigator or qualified designee and found to be acceptable prior to each dose of trial treatment.

Table 5: Laboratory Tests

Hematology	Chemistry	Urinalysis	Other
Hematocrit	Albumin	Blood	Serum β -human chorionic gonadotropin†
Hemoglobin	Alkaline phosphatase	Glucose	(β -hCG)†
Platelet count	Alanine aminotransferase (ALT)	Protein	PT (INR)
WBC (total and differential)	Aspartate aminotransferase (AST)	Specific gravity	aPTT
Red Blood Cell Count	Lactate dehydrogenase (LDH)	Microscopic exam (If abnormal)	Total triiodothyronine (T3)
Absolute Neutrophil Count	Carbon Dioxide ‡	results are noted	Free tyroxine (T4)
Absolute Lymphocyte Count	(CO_2 or bicarbonate)	Urine pregnancy test †	Thyroid stimulating hormone (TSH)
	Uric Acid		Blood for correlative studies
	Calcium		
	Chloride		
	Glucose		
	Phosphorus		
	Potassium		
	Sodium		
	Magnesium		
	Total Bilirubin		
	Direct Bilirubin (If total bilirubin is elevated above the upper limit of normal)		
	Total protein		
	Blood Urea Nitrogen		

† Perform on women of childbearing potential only. If urine pregnancy results cannot be confirmed as negative, a serum pregnancy test will be required.

‡ If considered standard of care in your region.

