7.1.6.4 Retreatment Phase

Subjects who stop pembrolizumab with SD or better may be eligible for up to one year of additional pembrolizumab therapy if they progress after stopping study treatment. This retreatment phase is only available if the study remains open and the subject meets the following conditions:

Either

- Stopped initial treatment with pembrolizumab after attaining an investigator-determined confirmed CR according to RECIST 1.1 (Section 14.3), and
 - Was treated for at least 24 weeks with pembrolizumab before discontinuing therapy
 - Received at least two treatments with pembrolizumab beyond the date when the initial CR was declared

OR

- Had SD, PR or CR and stopped pembrolizumab treatment after 24 months of study therapy for reasons other than disease progression or intolerance

AND

- Experienced an investigator-determined confirmed radiographic disease progression after stopping their initial treatment with pembrolizumab
- Did not receive any anti-cancer treatment since the last dose of pembrolizumab
- Has a performance status of 0 or 1 on the ECOG Performance Scale
- Demonstrates adequate organ function as detailed in Section 5.1.2
- Female subject of childbearing potential should have a negative serum or urine pregnancy test within 72 hours prior to receiving retreatment with study medication.
- Female subject of childbearing potential should be willing to use 2 methods of birth control or be surgically sterile, or abstain from heterosexual activity for the course of the study through 120 days after the last dose of study medication (reference Section 5.5.2). Subjects of child bearing potential are those who have not been surgically sterilized or have been free from menses for $>$ 1 year.
- Male subject should agree to use an adequate method of contraception starting with the first dose of study therapy through 120 days after the last dose of study therapy.
- Does not have a history or current evidence of any condition, therapy, or laboratory abnormality that might interfere with the subject's participation for the full duration of the trial or is not in the best interest of the subject to participate, in the opinion of the treating investigator.

Subjects who restart treatment will be retreated at the same dose and dose interval as when they last received pembrolizumab. Treatment will be administered for up to one additional year. Subjects should be re-consented prior to start of re-treatment.

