7.2.1.2 Serious Adverse Event (SAE)

A serious adverse event is any untoward medical occurrence resulting in one or more of the following:

- Results in death or ANY death occurring within 90 days of last dose of study drug (even if it is not felt to be drug related)
- Is life-threatening (defined as an event in which the patient was at risk of death at the time of the event; it does not refer to an event which hypothetically might have caused death if it were more severe)
- Requires inpatient hospitalization or prolongation of existing hospitalization

NOTE: Hospitalizations that are not considered SAEs are:

- Hospitalization planned prior to first administration of study drug
- Hospitalization for elective treatment of a pre-existing condition unrelated to the study medication
- Results in persistent or significant disability/incapacity
- Is a congenital anomaly or birth defect
- Is an important medical event (defined as a medical event(s) that may not be immediately life-threatening or result in death or hospitalization but, based upon appropriate medical and scientific judgment, may jeopardize the patient or may require intervention (e.g., medical, surgical) to prevent one of the other serious outcomes listed in the definition above). Examples of such events include, but are not limited to, intensive treatment in an emergency room or at home for allergic bronchospasm; blood dyscrasias or convulsions not resulting in hospitalization; or the development of drug dependency or drug abuse.
- Pregnancy

- Pregnancy of a patient or of the female partner of a male patient during the study or within 120 days after the last dose of study drug should be reported via an SAE report. Should pregnancy occur in a female participant during the treatment period, study drug should be discontinued and Merck notified immediately. Should a pregnancy occur in a female companion of a male participant during the treatment period, the male participant can continue treatment and Merck notified immediately. Any such pregnancy is to be followed until final outcome. Evaluating Adverse Events
- In addition to the above criteria, AEs meeting either of the below criteria, although not serious per ICH definition, are reportable to Merck in the same time frame as SAEs to meet certain local requirements. Therefore, these events are considered serious by Merck for collection purposes.
 - Is a new cancer (that is not a condition of the study)

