7.3 Participating Site Reporting Responsibilities

7.3.1 Reporting SAEs, ECIs and Pregnancy to the Coordinating Center (IU Simon Comprehensive Cancer Center)

Any serious adverse event, unanticipated problem, event of clinical interest or pregnancy occurring from the first dose of vorinostat to within 90 days from the last dose of study drug must be reported to the IU Simon Comprehensive Cancer Center within 24 hours of notification or discovery of the incident, using the MedWatch Form 3500A (Mandatory Reporting). This form must be accompanied by a cover letter which: identifies the event, is signed by the local principal investigator or treating physician, includes the applicable study number and title, and contains the following:

- Site assessment of the event attribution to investigational treatment or study procedure
- Site assessment of event expectedness (expected vs. unexpected)

- Assessment of whether or not the research places subjects at a greater risk of harm than was previously known or recognized
- Assessment of the event's affect on the risk to benefit ratio
- Statement as to whether the informed consent statement should reflect changes in the potential risks involved
- Statement as to whether the event has been reported previously, and if so, whether the frequency is considered unusually high

Send to: IUSCC Clinical Trials Office
 ATTN: Multicenter coordinator/ IUSCC-0551
 Preferred E-mail: [contact]
 Backup [contact]

All SAEs must also be entered into OnCore for **monthly review** by the DSMC Coordinator. The Multicenter Network Administrator, or designee, will distribute all reports meeting expedited reporting criteria to all participating sites, the FDA and to Merck. Copies of all serious adverse event reports will be kept on file in the IU Simon Comprehensive Cancer Center Clinical Trials Office.

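### Schedule footnote 5 is looser than inclusion 7 on the baseline pregnancy test, and section 7.3.1 gives pregnancy a shorter reporting window than section 7.2.1.2

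*Combined protocol and SAP*

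**What the plan says.** **Testing.** In section 6.0 the pregnancy-test row has a screening cell and one on-treatment cell, both marked with footnote 5. The footnote reads "Only if clinically indicated and must be completed" at most 7 days before the first dose. Inclusion 7 (section 5.1.1), under a lead-in that makes the list binding, says a female subject of childbearing potential "should have a negative urine or serum pregnancy test within 72 hours prior to receiving the first dose of study medication". The note to Table 5 in section 7.1.3 says "Perform on women of childbearing potential only". The retreatment criteria in section 7.1.6.4 use the 72-hour standard again: such a subject "should have a negative serum or urine pregnancy test within 72 hours prior to receiving retreatment with study medication".

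**Reporting.** Section 7.3.1 tells sites to notify the coordinating center within 24 hours of several kinds of safety report, and its list closes with "or pregnancy occurring from the first dose of vorinostat to within 90 days from the last dose of study drug". Section 7.2.1.2 says that a pregnancy in a patient, or in a male patient's partner, "during the study or within 120 days after the last dose of study drug should be reported via an SAE report". Section 5.5.2 asks for birth control from consent "throughout the study period up to 120 days after the last dose of study therapy". Exclusion 14 (section 5.1.2) covers pregnancy and plans to conceive or father a child "starting with the pre-screening or screening visit through 120 days after the last dose of trial treatment".

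**The concern.** The schedule is the page a site coordinator works from. Someone who follows footnote 5 literally could leave out the baseline test because nothing clinical prompted it, or accept a result too old for inclusion 7. Either would enter a woman without the evidence that the eligibility criterion asks for, and section 5.5.2 warns that both drugs may harm a fetus.

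On reporting, section 7.3.1 is the site's instruction for notifying the coordinating center. It names pregnancy and sets a limit 30 days before the end of the period in which section 7.2.1.2 wants pregnancies reported and section 5.5.2 wants contraception used.

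**Working it through.** This is a comparison of texts. The plan states no computed figure on this point, and the only arithmetic is the difference between stated windows and a ceiling on who could be tested.

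| Item | Looser text | Stricter text | Difference |
|---|---|---|---|
| Is the baseline test required? | Footnote 5: conditional on clinical indication | Inclusion 7: every woman of childbearing potential | Required v conditional |
| Age of the test at first dose | Footnote 5: up to 7 days | Inclusion 7: up to 72 hours = 3 days | 7 − 3 = 4 days |
| Pregnancy report, time after last dose | Section 7.3.1: 90 days | Section 7.2.1.2: 120 days | 120 − 90 = 30 days (days 91 to 120) |

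1. *Can footnote 5 be read so that it agrees with inclusion 7?* The clinical-indication phrase may have been written for the on-treatment cell. But the same sentence sets a limit before the first dose, which fits only a pre-treatment test, and the mark is printed on the screening cell. The phrase may instead be shorthand for childbearing potential. That would remove the conflict over whether the test is required, but 7 days against 72 hours would remain.

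2. *Does other procedural text restore the 72 hours?* No. Section 7.1.3 and footnote 9 give a general 10-day window for screening laboratory tests. The Table 5 note limits who is tested; it sets no timing and does not itself require a screening test. For the first dose, the 72-hour limit stands in inclusion 7.

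3. *Which texts on reporting agree?* Sections 7.2.1.2 and 5.5.2 and exclusion 14 all use 120 days after the last dose. Section 7.3.1 uses 90 days. Section 7.2.3 differs again: 120 days counted from completing the trial, or 30 days after treatment stops if new anticancer therapy begins, whichever comes first.

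4. *How many participants could this touch?* The test can concern only women of childbearing potential outside the prostate cohort. Planned enrollment there is 2 × 3 + 30 = 36 to 2 × 6 + 30 = 42 (section 8.4), before any replacements. That is a ceiling on the group and does not count affected women. Reporting also covers partners of male participants. The documents give neither number, so no count of affected people is possible.

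**The case against.** The case for leaving the text alone has real weight. The windows are nested, so a site that follows the stricter rule meets both. Section 7.1 describes the schedule as a summary. Section 7.1.1.2 has the investigator or a designee review every criterion, and under section 10.3 the coordinating center checks the eligibility checklist and source documents before registration. A reader might infer that women will be enrolled untested. The documents do not support that, since several checks would have to fail first. These checks contain most of the testing risk, but they leave the footnote contradicting the criterion.

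A reader might also infer that a pregnancy on days 91 to 120 will go unreported. That does not follow either. Section 7.3.1 does not say later pregnancies need not be reported. Section 7.2.3 separately makes investigators responsible for reporting pregnancies to the sponsor within 24 hours and to the drug supplier within 2 working days. Section 5.5.3 requires partner pregnancies to be reported to both, with no 90-day limit. Section 7.2.1.2 itself runs to 120 days. This part of the objection stands: the fault is a misaligned instruction, and no loss of reports is shown. One limit applies. For a participant who starts new therapy, the section 7.2.3 window can close at 30 days, so that route does not cover everyone to day 120.

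Finally, the new-therapy cut-off in section 7.2.3 might be taken as a third error. Section 7.2.4 has a similar kind of cut-off for events of clinical interest, so it may be deliberate. It is a question for the sponsor.

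**Conclusion.** Both inconsistencies are in current operative text and are wrong as written. Footnote 5 allows a test 4 days older than inclusion 7 permits and, on its plain wording, makes a required test conditional. Even on the most favorable reading, the 4-day conflict remains. Section 7.3.1 stops 30 days short of section 7.2.1.2 for pregnancy.

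Severity is low. These figures are differences between stated windows; they do not estimate missed tests or missed reports. Few participants are likely to be affected, and no efficacy or safety estimate changes. The conclusion assumes that inclusion 7 is mandatory despite its softer verb, because its lead-in makes the list a condition of eligibility. It also assumes that 120 days is the intended pregnancy window, because three other places in the protocol use it.

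**What to change.** - **Footnote 5.** Replace with: *Women of childbearing potential: required at screening, within 72 hours before the first dose of study drug (including a run-in dose); repeat on treatment only if clinically indicated.*
- **Section 7.3.1.** Have sites report pregnancy in a patient or in a male patient's female partner to 120 days after the last dose of study drug, and keep 90 days for other serious adverse events and events of clinical interest. State the pregnancy exception in words, because section 7.2.1.2 lists pregnancy among serious adverse events.
- **Query to the sponsor on section 7.2.3.** Is the cut-off at 30 days after treatment, when new therapy starts, intended for pregnancy? If so, say so in sections 7.2.1.2 and 7.3.1 as well. If not, align section 7.2.3 so that reporting never ends before 120 days after the last dose, and keep its end-of-trial limit where that runs later.

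The cost is two corrected lines and one sponsor decision, which may bring small matching edits to sections 7.2.1.2 and 7.2.3. No visit or test is added, because inclusion 7 and section 7.2.1.2 already impose the stricter duties.
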